The Use of Acthar (ACTH) in Patients with Focal Segmental Glomerulosclerosis (FSGS) Who Have Developed Chronic Kidney Disease Stage V (CKD) or End Stage Renal Disease (ESRD) and Are Undergoing a Renal Transplant

Principal Investigator: [name]., MPH
Ph. [contact]
Email: [contact]

COMIRB 17-2336

Version Date: July 11, 2018

I. Hypotheses and Specific Aims

This is an open-label pilot study where all subjects will be treated with the drug, Acthar. The specific aim is to determine the rate of recurrent FSGS through evaluation of kidney biopsies performed post renal transplantation. FSGS is a type of nephrotic syndrome that can recur aggressively after renal transplantation. When FSGS recurs after transplant it increases patient morbidity and increases graft loss.

It is believed that ACTH, besides steroid dependent properties, has steroid independent properties (see figure 1 on page 10). With the steroid independent properties it may stimulate the MCIR receptor which affects not only the podocytes, but also the T-cells, B-cells, NK-cells and APC-cells.

The primary end-point is to measure proteinuria prior (if patient still makes urine) and after renal transplantation and determine the change in proteinuria and the recurrence of FSGS as seen in kidney transplant biopsy. Kidney transplant biopsies will be performed at time 0 (at implantation), 3 months and 12 months post transplantation. Our hypothesis is that the use of Acthar, on patients with history of FSGS as cause of chronic kidney disease, at the time of renal transplantation and for a 6-month period of time following transplant, decreases the probabilities of patients developing recurrent disease after renal transplantation.

Our secondary end point is to evaluate renal function after transplantation as measured by eGFR. We hypothesize that patients will maintain a stable eGFR and creatinine while on Acthar and after it is stopped.

II. Background and Significance

Wait time for kidney transplantation is on average at least 5 years and unfortunately many patients die while waiting for kidney transplantation. Recurrent disease affects 23-30% of renal transplant recipients with FSGS. No

COMIRB 17-2336
P.I. [name]
Version 7-11-2018

known genetic mutations have been identified among those with recurrence. Plasmapheresis has resulted in complete or partial remission in 75% of those with recurrence after transplant but this treatment is very aggressive as it increases bleeding risk and involves the placement of a catheter. Furthermore, it is performed usually three times a week for months in order to achieve remission. Modern immunosuppression does not reduce the rate of recurrent FSGS (1). Moreover, recurrence after transplantation, where the patient is already immunosuppressed, is a poor prognostic factor and it brings a high risk of graft failure.

Typically, recurrence of primary FSGS occurs early in the post transplantation period with heavy proteinuria and progressive renal insufficiency and graft failure. Current animal and human data suggest that primary FSGS is likely to be initiated by podocyte injury; however, Savin *et al.* (2) described a circulating plasma factor and its association with many cases of primary and recurrent FSGS. The rapid nature of recurrent FSGS after transplantation is consistent with the theory that one or more circulating factors may be playing a major role in the pathogenesis of recurrence (3).

Acthar is FDA approved for the treatment of nephrotic syndrome. The FDA package insert of Acthar: “To induce a diuresis or a remission of proteinuria in the nephrotic syndrome without uremia of the idiopathic type or that due to lupus erythematosus.” (3). It still has not been studied in renal transplant patients, but clinical data in our center has been very encouraging and it has been used safely and effectively in renal transplant recipients with FSGS.

This medication has been studied in nephrotic syndrome in native kidney disease. Most studies have used a dose of 80 units twice a week (one cc of the medication contains 80 units). There is no data on the renal transplant population, but is interesting to note that with the steroid independent properties, Acthar may target several cell lineages that are relevant in transplantation and maybe a reason of why this medication can work to decrease recurrence after transplantation.

Recent data has shown an etiologic role of perturbations of the CD40 antigen in recurrent FSGS (4). It is unknown if Acthar would change CD40 in patients with FSGS. As part of our research investigation, we propose to investigate CD40 in kidney biopsies, by immunohistochemistry, and serum of patients, by ELISA. Patients will have one pre-transplant serum sample which will be measured for CD40 by utilizing the CD40 antibody through ELISA. A 2nd blood sample will be obtained at 3 months post transplant, at 6 months post transplant and at 1 year post transplant. This blood will be drawn with standard of care labs, so it would not impose additional blood draws to the patient.

We expect from 7-10 patients a year to meet inclusion criteria.

III. Research Methods and Design

A. Study Type/Design:

Prospective open-label study enrolling renal transplant recipients with the primary native kidney disease of FSGS. This protocol already has an IND exemption as this medication is FDA approved for the treatment of nephrotic syndrome. All subjects will receive Acthar.

B. Endpoints

The primary endpoint is rate of recurrence of FSGS as seen in renal transplant biopsies and in rate of proteinuria.

The secondary endpoints are duration of remission after Acthar treatment (Time Frame: 1 year and 2 years of study follow-up after treatment completion), changes in kidney fibrosis after Acthar treatment and safety and efficacy of Acthar in the post renal transplant population.

C. Patient Recruitment

Preliminary data was previously submitted in the American Transplant Congress 2017. Post renal transplant recipients that developed FSGS were treated with Acthar at the discretion of the investigator. Half of the patients experienced reductions in proteinuria. Prior to the introduction of this medication, developing recurrent FSGS in the renal transplant meant that the renal transplant would likely be lost within a year.

This is a single center pilot study where the target subject number is 20 patients and the target population is primary FSGS patients. By the current data, FSGS should recur in 23-30% of patients. Therefore, it would be expected that at least 4 patients will develop recurrent FSGS after renal transplantation.

After we obtained data from this pilot study we would expect to request funding for a large multicenter study.

Inclusion Criteria:

1. Adult renal transplant recipients with primary FSGS
2. Ability to consent

Exclusion Criteria:

1. Renal transplant recipients whose primary disease is not FSGS

2. Patients who are receiving dual organ transplants
3. Patients who have been on Acthar prior to transplantation.
4. Intractable CHF (congestive heart failure)
5. Uncontrolled hypertension defined as BP >180/100
6. Uncontrolled diabetes defined as a HgbA1c>10%
7. An acute infection
8. Allergies to pig-derived proteins
9. Have received a live vaccine three months prior to transplant
10. Cushing's syndrome
11. Addison's disease
12. Previous intolerance to native ACTH or proteins of porcine origin
13. History of scleroderma, osteoporosis, systemic fungal infections, ocular herpes simplex, recent surgery, history of or the presence of peptic ulcer, primary adrenocortical insufficiency or adrenocortical hyperfunction.
14. Recent cardiovascular event within 3 months of screening including: Myocardial Infarction, CVA, TIA, New York Heart Association Functional Class III or IV failure, Obstructive valvular heart disease, or hypertrophic cardiomyopathy, second or third degree atrioventricular block not successfully treated with a pacemaker.
15. History of HIV
16. New diagnosis of cancer or recurrent cancer within 2 years of screening
17. History of alcohol or drug abuse within 12 months of study entry.
18. Receipt of any investigational drug within 30 days of enrollment.
19. Psychiatric disorder that interferes with the patient's ability to comply with the protocol.
20. Poorly controlled diabetes with an HbA1C > 10%
21. Type 1 diabetes mellitus
22. Pregnancy

D. Treatment Overview

Screening will be performed by the Principal Investigator during the kidney transplant evaluation clinics and during the wait list kidney transplant evaluation clinic. All patients with FSGS will have induction therapy with thymoglobulin and maintenance immunosuppression with tacrolimus and mycophenolate. This is the standard regimen that we utilize post transplant in all our recipients.

E. Dosage and Administration of Acthar

The dose of Acthar to be given to every enrolled patient will be 80 units twice a week for 6 months. The first dose of Acthar is given at the time of transplantation and will be continued, twice a week, for 6 months. See Appendix A (page 9) for additional details.

Safety:

1. Acthar should always be injected beneath the skin or into the muscle.
2. Never inject Acthar directly into a vein.

Risks:

1. Development of high blood sugars (10%)
2. Development of high blood pressure (11%)
3. Edema (1%)
4. Mood and behavior changes (7%)
5. Weight and appetite changes (1%)

We will be monitoring all patients at the stated time points for all the above risks and side effects. We will be monitoring side effects with our research transplant coordinator and the PI who will be seeing the patients. We will also have a safety officer, [name], who will be reviewing the adverse events. At every clinic visit, as standard of care, patients get their vital signs taken as well as urinalysis and laboratories. We will be reviewing all the results carefully and assess every patient to see if there are any signs of infection. [name] will also be part of the DSMB. While [name] will review safety data and adverse events every three months, the DSMB, of which she will be a member, will meet every 12 months.

F. Laboratory Testing and Study Schedule

Patients will have one pre-transplant serum sample which will be measured for CD40 Ab. A 2nd blood sample will be obtained at 3 months post transplant, 6 months post transplant and at 1 year post transplant. This blood will be drawn with standard of care labs, so it would not impose additional blood draws to the patient.

Standard of care labs include CBC, BMP, tacrolimus level, BK PCR plasma, CMV PCR plasma, DSA, Allosure testing and urine protein/creatinine.

- The first month post transplant, patients will have labs and clinic visit biweekly.
- The second month post transplant patients will have labs and clinic visit weekly.
- The third month post transplant patient will have labs weekly and clinic visit every other week.
- From the 4th till the 6th month post transplant patients will have labs every other week and clinic visit monthly.

- From month 6 till month 12 patients will have labs monthly and clinic visit every other month.

[name], a nephrologist and immunologist, will be helping in the testing of CD40 Ab. ELISA will be used in patient's serum to test for CD40. In addition, human kidney biopsy tissues will be fixed in formalin or AFA (alcohol–formalin–acetic acid) solution and embedded in paraffin. For CD40, antigen retrieval was performed by proteinase K digestion and then hydrolysis by heating in a microwave oven with citrate buffer. The rabbit polyclonal primary anti-CD40 Ab (Anti-CD40 Ab 11E9, Abcam) will be diluted at 1:150 and incubated overnight at +4°C. A three-step technique will be used with biotinylated anti-rabbit secondary Ab, avidin-biotin-peroxidase complex as the vector, and 3,3'-diaminobenzidine (DAB) as the substrate.

G. Patient Monitoring and Evaluation

Patients will have a kidney biopsy at time 0 (at the time of implantation), 3 months and 12 months. If at any other time it is clinically necessary to perform another biopsy it will be performed. Any extra kidney transplant tissue will be used to stain for CD40 Ab. This would not impose an extra risk as it will be part of the standard of care kidney transplant biopsy. We will be collecting clinical data from the patient's medical record including medications, CBC, CMP, urine protein/creatinine, BK, CMV, adverse events, infections and any hospital admissions.

H. Potential Pitfalls and Contingencies

We will ideally attempt to avoid plasmapheresis after renal transplantation, but if a patient develops severe proteinuria will start plasmapheresis and monitor proteinuria until it decreases. If there is no change in proteinuria after a month on plasmapheresis, we will stop plasmapheresis and continue only with Acthar.

- I. Specific participant and study stopping criteria:
 1. Development of severe hypertension defined as BP > 180/100
 2. Development of congestive heart failure
 3. Severe edema that is impeding ability to breath
 4. Withdrawal of consent
 5. Pregnancy
 6. Use of immunosuppressive drugs other than those specified by the protocol except those needed to treat FSGS and proteinuria
 7. Any other protocol deviation that results in significant risk to the patient's safety.

J. Data Processing and Analysis

Sample size: A sample size of 20 data pairs (for example from immediately post-transplant to 12 months post-transplant) achieves 80% power to detect an effect size of change in proteinuria of 0.66 standard deviations with a significance level (alpha) of 0.05 using a two-sided paired t-test. A sample size of 20 produces an exact two-sided 95% confidence interval from 0.087 to 0.491 when the recurrent FSGS proportion is 0.25, i.e. 5/20 patients. If only 4/20 patients develop recurrent FSGS the 95% confidence interval would be 0.057 to 0.437 and if 3/20 patients developed FSGS the 95% confidence interval would be 0.032 to 0.379. This lack of precision in the estimate of the proportion of patients developing recurrent FSGS is due to the small sample size. However, this is a pilot study to determine whether Acthar helps decrease the rate of recurrent FSGS after renal transplantation. The observed rate of recurrent FSGS in patients treated with Acthar will be used to power larger, multicenter studies. We will seek expert opinion from the participating centers regarding expected rates when planning the trial. The outcomes which will be used to plan for a future, larger, more definitive trial will include recurrent FSGS as observed in this pilot study as well as change in proteinuria over time.

Data analysis: Data will be analyzed using two-sided paired t-tests for comparing two time points as well as mixed effects models for multiple time points, to assess changes in proteinuria over time. Other clinical, pathological and laboratory variables may be included in the models to determine whether the change over time is affected by these covariates. Similar methods will be used to model changes in eGFR over time. The observed proportion of patients developing recurrent FSGS will be reported as a proportion with an exact 95% confidence interval. Standard of care labs including CBC, BMP, tacrolimus level, BK PCR plasma, CMV PCR plasma, DSA, Allosure testing and urine protein/creatinine as well as biopsy findings will be reported as summary statistics (means \pm SD, medians (with interquartile range) and proportions as appropriate) at each time point.

All patient information will be de-identified for study purposes.

We will monitor the data and safety measures periodically. We will monitor AEs on a weekly basis.

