Appendix A – Acthar (ACTH) Study Visit Schedule

| | SCR | OR | Day | | | | | | | | Week | | | | Month | | | | | | | | | | | | |
|--|-------|----|-----|---|----|----|----|----|----|----|------|---|---|---|-------|---|---|---|---|---|---|----|----|----|----|----|---|
| | -21-0 | 0 | 4 | 7 | 10 | 14 | 18 | 21 | 25 | 28 | 5 | 6 | 7 | 8 | 3 | 4 | 5 | 6 | 7 | 8 | 9 | 10 | 11 | 12 | 18 | 30 | |
| Informed consent | x | | | | | | | | | | | | | | | | | | | | | | | | | | |
| Background information | x | | | | | | | | | | | | | | | | | | | | | | | | | | |
| Inclusion/exclusion | x | | | | | | | | | | | | | | | | | | | | | | | | | | |
| Medical History | x | | | | | | | | | | | | | | | | | | | | | | | | | | |
| Transplant information | | x | | | | | | | | | | | | | | | | | | | | | | | | | |
| Pregnancy test | x | | | | | | | | | | | | | | | | | | | | | | | | | | |
| Vital signs | x | x | x | x | x | x | x | x | x | x | x | x | x | x | x | x | x | x | x | x | x | x | x | x | x | | |
| Physical exam | x | x | x | x | x | x | x | x | x | x | x | x | x | x | x | x | x | x | x | x | x | x | x | x | x | | |
| Laboratory tests *1 | x | x | x | x | x | x | x | x | x | x | x | x | x | x | x | x | x | x | x | x | x | x | x | x | x | | |
| Renal Biopsy | | x | | | | | | | | | | | | | x | | | | | | | | | | x | | |
| Study medication *2 | | x | x | x | x | x | x | x | x | x | x | x | x | x | x | x | x | x | | | | | | | | | |
| CD40 Ab *3 | x | | | | | | | | | | | | | | x | | | x | | | | | | | x | | |
| Follow-up (for secondary data on remission: yes or no) | | | | | | | | | | | | | | | | | | | | | | | | | | x | x |
| | | | | | | | | | | | | | | | | | | | | | | | | | | | |
| | | | | | | | | | | | | | | | | | | | | | | | | | | | |
| | | | | | | | | | | | | | | | | | | | | | | | | | | | |

*1 All laboratories (except CD40 Ab – see footnote *3) are part of SOC/Standard of Care. SOC labs include CBC, BMP, tacrolimus level, BK PCR plasma, CMV PCR plasma, DSA, Allosure and urine protein/creatinine.

*2 Study medication (Acthar) will continue twice a week through month 6 post-transplant.

*3 CD40 Ab which will be measured pre transplant, at 3, 6 and 12 months. This laboratory will be drawn at the same time as SOC labs so that patient does not have an additional blood drawn. [name] will assist with the testing of the CD40 Ab.

Figure 1

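### The fibrosis secondary endpoint has no stated score, baseline or interval, no scheduled biopsy marks the end of treatment, and the analysis section plans no within-patient change for it

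*Combined protocol and SAP*

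**What the plan says.** The endpoint is in Section III.B: "changes in kidney fibrosis after Acthar treatment and safety and efficacy of Acthar in the post renal transplant population". Fibrosis is named nowhere else in the document, and no score, baseline visit or time frame is attached to it. The remission endpoint in the same sentence does carry a time frame: "duration of remission after Acthar treatment (Time Frame: 1 year and 2 years of study follow-up after treatment completion".

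On treatment, Section III.E states: "The first dose of Acthar is given at the time of transplantation and will be continued, twice a week, for 6 months". Footnote 2 of Appendix A agrees: "Study medication (Acthar) will continue twice a week through month 6 post-transplant".

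On biopsies, Section III.G states: "Patients will have a kidney biopsy at time 0 (at the time of implantation), 3 months and 12 months". Section I gives the same three times. Beyond these, Section III.G allows only biopsies for clinical need: "If at any other time it is clinically necessary to perform another biopsy it will be performed".

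On analysis, Section III.J applies paired t-tests and mixed effects models to proteinuria and extends similar methods to eGFR. Pathological variables appear there as possible covariates. For biopsies as outcomes, the only statement is that the standard laboratory results "as well as biopsy findings will be reported as summary statistics", given separately for each time point.

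**The concern.** An endpoint worded as a change needs a measure, a starting point, an end point and an estimator. For fibrosis none of the four is fixed, and the biopsy times and the drug period do not line up on one natural reading of the wording.

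Two things are at stake. First, the interval could be chosen after the data are seen, or a change since implantation could be reported as a change after the drug was stopped. Second, a reader given only a mean and standard deviation at 0, 3 and 12 months cannot recover the precision of the change. If some 12-month biopsies are missing, the reader also cannot tell whether a difference between visits reflects change in kidneys or a different set of kidneys. The time-0 biopsy is taken at implantation, so it describes the graft as received, and grafts may differ at that point.

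**Working it through.** **1. Which changes the schedule supports.** Inputs: drug from 0 to month 6 (Section III.E; Appendix A, footnote 2); biopsies at 0, 3 and 12 months (Sections I and III.G). In the Appendix A table as read, the last biopsy mark sits one column past month 12, but the follow-up marks are shifted by the same one column, so I take month 12 from the text.

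| Interval | Relation to Acthar | Obtainable? |
|---|---|---|
| 0 to 3 months | on treatment throughout | yes |
| 0 to 12 months | 6 months on, 6 months off | yes |
| 3 to 12 months | 3 months on, 6 months off | yes |
| 0 to 6 months | exactly the treatment period | no, no biopsy at month 6 |
| 6 to 12 months | off treatment only | no, no biopsy at month 6 |

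**2. The plan's own figures.** Section III.J gives none for fibrosis. Its stated power is for proteinuria: 20 pairs, 0.66 standard deviations, two-sided alpha 0.05. A noncentral t with 19 degrees of freedom and noncentrality 0.66 × √20 gives 0.7995, against 80% stated, so it reproduces. It neither supports nor weakens the present point.

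**3. What visit summaries leave out, with complete data.** With 20 complete pairs the difference between visit means equals the mean paired change. Its precision does not follow from the visit summaries. With equal standard deviation S at both visits and within-patient correlation r,

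SD of change = S × √(2(1 − r)); 95% half-width = t(0.975, 19) × SD of change / √20 = 0.468 × √(2(1 − r)) × S.

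The documents do not give r, so I show a range:

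- r = 0: 0.468 × 1.414 = 0.66 S
- r = 0.5: 0.468 × 1.000 = 0.47 S
- r = 0.9: 0.468 × 0.447 = 0.21 S

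The same visit table is compatible with roughly a threefold range of precision (0.66 / 0.21 ≈ 3.1).

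**4. What happens if 12-month biopsies are missing.** Let n patients have a time-0 biopsy and m of them have no 12-month biopsy. Then

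(12-month mean of those biopsied) − (time-0 mean of all) = (mean paired change in those with both) + (m/n) × (time-0 mean of those with both − time-0 mean of those missing).

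The last term is a change of patient mix, not a change in any kidney. The documents give no fibrosis values and no rate of missing biopsies, so the following is only an illustration of the range. Take n = 20, m = 4 and nobody changing:

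- missing kidneys 12.5 points higher at time 0 (20 against 7.5): all 20 average (16 × 7.5 + 4 × 20)/20 = 10.0, the remaining 16 average 7.5, apparent change −2.5
- missing kidneys the same as the rest: apparent change 0
- missing kidneys 12.5 points lower (7.5 against 20): all 20 average (16 × 20 + 4 × 7.5)/20 = 17.5, the remaining 16 average 20, apparent change +2.5

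Size and sign depend wholly on which kidneys are missing.

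**5. What pairing would deliver.** The half-width for the mean paired change is 0.47 standard deviations of the change with 20 pairs and 0.53 with 16.

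**The case against.** The strongest reply is that the endpoint is derivable. Treatment starts at transplantation, a biopsy is taken at implantation and another at 12 months, after treatment has ended. Change between those two is an ordinary reading of the phrase. This stands. A reader might infer that the endpoint cannot be derived at all, and the documents do not support that. The remission endpoint's time frame makes the reading from treatment completion plausible but does not impose it on fibrosis. What remains is that the protocol does not say which reading applies, and one of the two has no baseline biopsy.

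Other tempting inferences also fail:

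- That Section III.J analyses no change. It does, for proteinuria and eGFR; the gap concerns biopsy findings.
- That visit means will drift towards apparent improvement because the most fibrotic grafts are lost first. The documents link graft loss to recurrent FSGS, not to fibrosis at implantation. With complete pairs the shift is zero.
- That biopsies for clinical need will be mixed with scheduled ones. Summaries are planned by time point, and no mixing is shown.
- That the sponsor will report the result as a drug effect. The text does not say so. The study is single-arm, so pairing could not establish such an effect either.

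It is also fair that this is a secondary endpoint in a 20-patient pilot, and that Section III.J names recurrence and proteinuria, not fibrosis, as the outcomes for planning the larger trial. That limits the weight of the point but does not supply the missing definition or estimator.

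**Conclusion.** The point holds in a limited form. From the documents alone: fibrosis has no stated score, baseline or interval; change from treatment end to month 12 cannot be obtained from scheduled biopsies; changes from 0 to 3 and 0 to 12 months can; and the only analysis covering biopsy findings is a summary at each visit, which gives no precision for within-patient change.

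The threefold range in precision rests on equal standard deviations at the two visits and correlations from 0 to 0.9, both assumed. The effect of missing 12-month biopsies is real as a mechanism, but its size and direction are unknown from the documents; the figures of −2.5 to +2.5 points illustrate it and do not estimate it. The primary endpoint is not affected.

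**What to change.** In Section III.B, define the endpoint as within-patient change in a named fibrosis score from the implantation biopsy to the 12-month protocol biopsy, with 0 to 3 months as the on-treatment change. If the sponsor does mean change since the end of treatment, the endpoint and the biopsy schedule must be reconciled.

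In Section III.J, report the mean paired change with a 95% confidence interval in patients who have both biopsies. Beside it, list every patient without a 12-month biopsy, with the time-0 score, the 3-month score if available, and the reason. Describe the result as change since implantation, not as an Acthar effect or an off-treatment change.

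The cost is wording and a narrower claim; no added biopsy, visit or patient is needed. Pairing removes the change in patient mix but not the selection that arises if grafts are lost because they progress, so the list must always accompany the estimate.

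### The proteinuria analyses include values after rescue treatment and lose unpaired patients without saying so, so the change in proteinuria can look better than it would without rescue

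*Combined protocol and SAP*

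**What the plan says.** Sections I and III.B make proteinuria part of the primary endpoint, together with recurrence on biopsy. All patients receive Acthar; there is no control arm.

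Section III.H covers rescue: "if a patient develops severe proteinuria will start plasmapheresis and monitor proteinuria until it decreases". No threshold for severity is given. The same section states a preference against using it: "We will ideally attempt to avoid plasmapheresis after renal transplantation". Section III.I makes non-protocol immunosuppression a stopping criterion but exempts drugs given for FSGS or proteinuria, so plasmapheresis is not the only permitted added treatment. Section II says "Plasmapheresis has resulted in complete or partial remission in 75% of those with recurrence after transplant". It also says "Typically, recurrence of primary FSGS occurs early in the post transplantation period with heavy proteinuria".

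Section III.J gives the analysis: "Data will be analyzed using two-sided paired t-tests for comparing two time points as well as mixed effects models for multiple time points". On covariates it says "Other clinical, pathological and laboratory variables may be included in the models". The sample-size paragraph says "A sample size of 20 data pairs (for example from immediately post-transplant to 12 months post-transplant) achieves 80% power", so that pair of time points is only an example. Laboratory results, including urine protein/creatinine, are to be summarised at each time point. The recurrence proportion gets an exact 95% confidence interval, and the observed rate is to be used to power larger studies. The outcomes for planning the larger trial "will include recurrent FSGS as observed in this pilot study as well as change in proteinuria over time".

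Nothing in III.J says whether proteinuria values after rescue are used, set aside or replaced, or how a patient with a lost graft or other missing value enters the analysis.

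**The concern.** The outcome triggers the rescue, and the rescue is expected to lower the outcome. A patient whose proteinuria becomes severe is treated for it, and the later, lower value then enters the before/after comparison as if only Acthar had been given. A patient whose graft is lost before the second time point contributes no pair, and losses to recurrence would tend to remove high values. Both mechanisms generally move the mean change in the favourable direction, and no control group shows by how much.

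The baseline matters. If proteinuria is low immediately after transplant, rescue hides a later rise. If early recurrence has already raised it, rescue produces a fall that reads as a drug effect. Because change in proteinuria is one of the outcomes that will inform the larger trial, the distortion can carry forward.

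**Working it through.** **1. The plan's own figures.** Paired t-test, n = 20, effect 0.66 SD, two-sided alpha 0.05: df = 19, noncentrality 0.66 x sqrt(20) = 2.95, power 0.799 (stated 80%). Exact 95% intervals: 5/20 gives 0.087-0.491, 4/20 gives 0.057-0.437, 3/20 gives 0.032-0.379. All match; nothing in this point disputes them.

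**2. Inputs.** From the documents: recurrence 23-30%, that is 20 x 0.23 = 4.6 to 20 x 0.30 = 6.0 patients if Acthar has no effect; remission with plasmapheresis 75%. Assumed: 25% recurrence (the plan's 5/20 case), 4 g/g in a recurrent patient, remission lowering that by half or completely and lasting to the second time point, and an SD of all other changes of 0.3, 1.0 or 2.0 g/g. The share of recurrences rescued is unknown, so it is varied.

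**3. Shift in the mean change.** Hidden share = share rescued x 0.75 x fraction by which remission lowers proteinuria. Shift = 0.25 x 4 g/g x hidden share = 1.00 g/g x hidden share.

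| Share rescued | Hidden share, halved | Hidden share, full remission | Shift in mean change (g/g) |
|---|---|---|---|
| 25% | 0.25 x 0.75 x 0.5 = 0.094 | 0.25 x 0.75 x 1 = 0.188 | 0.09 to 0.19 |
| 50% | 0.5 x 0.75 x 0.5 = 0.188 | 0.5 x 0.75 x 1 = 0.375 | 0.19 to 0.38 |
| All | 1 x 0.75 x 0.5 = 0.375 | 1 x 0.75 x 1 = 0.75 | 0.38 to 0.75 |

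Low baseline: a true mean rise of 1.00 g/g is seen as 1.00 - 0.09 = 0.91 at the mildest and 1.00 - 0.75 = 0.25 at the most severe. Raised baseline: a true mean change of 0.00 is seen as -0.09 to -0.75.

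**4. Chance of a significant false fall.** Simulation of the two-sided paired t-test, 40,000 trials per setting, n = 20. Each patient recurs with probability 0.25 and is then already at 4 g/g at baseline; Acthar has no effect; rescued patients remit with probability 0.75; other changes are normal with the SD shown. Each cell gives remission that halves proteinuria / full remission.

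| Share rescued | SD 0.3 | SD 1.0 | SD 2.0 |
|---|---|---|---|
| None | about 2.5% | about 2.5% | about 2.5% |
| 25% | 4.2% / 2.3% | 4.8% / 5.3% | 3.8% / 4.8% |
| 50% | 12.0% / 9.9% | 8.7% / 11.9% | 5.6% / 9.1% |
| All | 43.4% / 46.5% | 21.9% / 36.1% | 10.7% / 22.1% |

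**5. Lost pairs alone.** Low baseline, no rescue, five recurrences rising by 4 g/g: over all 20 the mean change is 5 x 4/20 = 1.00. If k of the five grafts are lost, the available pairs give (5 - k) x 4/(20 - k): 16/19 = 0.84, 12/18 = 0.67 and 8/17 = 0.47 for k = 1, 2, 3. If baseline was already raised and did not change, dropping lost grafts adds little bias. The documents give no graft-loss rate for treated patients, so k is purely illustrative.

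**The case against.** Several points on the other side stand.

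- Using values regardless of rescue is a legitimate choice. A reader might infer that the planned analyses are invalid. The documents do not support that: the choice is unstated and has no companion result, but it is not wrong.
- Biopsy-proven recurrence is the specific aim, has its own exact interval, and is the rate named for powering larger studies. Scheduled biopsies, plus any that are clinically necessary, make it much less sensitive to rescue. It would be wrong to read this point as undermining that proportion.
- Frequent urine protein/creatinine values, summarised by time point, would show a spike before rescue. They would not show who was rescued or when.
- The mixed model keeps the earlier values of a lost graft, but relies on missing at random. Covariate adjustment for plasmapheresis is permitted, not required, and would not by itself remove the bias, because rescue is triggered by the outcome.
- Without a control arm, no before/after change can be assigned to Acthar, with or without rescue. The fix does not cure that; it only makes visible how much of the result passed through rescue.
- The large percentages need every recurrence to be raised at baseline, every one rescued, and remission that lasts. The protocol hopes to avoid plasmapheresis. A reader might take 43-47% as the plan's error rate; it is the top of an assumed range, and it depends on the SD.

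**Conclusion.** The point holds for the proteinuria part of the primary endpoint. The direction follows from the documents: high proteinuria triggers treatment that the protocol expects to lower it, and the analysis takes the result as observed. The size does not follow from them. Under the stated assumptions, a significant false fall occurs in about 2-5% of trials if a quarter of recurrences are rescued. If all are rescued, it is about 43-47%, 22-36% or 11-22% at an SD of 0.3, 1.0 or 2.0 g/g. It tends to the nominal 2.5% if rescue is rare, and there is no floor above that. The power figure and the recurrence intervals are unaffected. The plan should be amended on this, but it is a matter of analysis text in a small pilot, not a flaw that prevents the study from being run.

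**What to change.** Leave the rescue rule unchanged and amend section III.J only.

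1. Keep the paired t-tests and mixed models as the main proteinuria analyses, and state that they include values after any rescue treatment.
2. Beside biopsy-proven recurrence, add a supportive proportion over all treated patients with an exact 95% CI. Count as failure by month 12 any of: recurrence on biopsy, plasmapheresis or another added treatment for FSGS or proteinuria, or graft loss to FSGS. Report separately the number whose outcome is missing through withdrawal, death or other graft loss, and show the proportion with these counted as failures and as non-failures. For example, 5/20 by biopsy (0.087-0.491) plus one patient rescued without a positive biopsy gives 6/20 (0.119-0.543). One further patient with a missing outcome would make the two bounds 6/20 and 7/20 (0.154-0.592).
3. Take the dates of rescue and graft loss from the medical record already being reviewed, and list the last urine protein/creatinine before each.
4. A worst-rank analysis of proteinuria change is optional. If used, label it a treatment-failure analysis, because with a raised baseline it can point to a rise that did not occur. It does not count everyone: withdrawals, deaths and other graft losses have no rank. It is also weak. With five failures ranked worst and the rest symmetric, the signed-rank sum is 90 + 120/2 = 150, against an expected 105 with SD 26.8, so z = 45/26.8 = 1.68 and p = 0.09. A non-significant result must not be read as no rise.

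The cost is a few sentences and two dates per affected patient, with no new visit, sample or change of treatment. The limitation is that rescue is an investigator decision in an open-label study with severity undefined, so the added results are supportive only.
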